### 7.3.2 Secondary analyses

The secondary analysis will evaluate safety, pharmacokinetics and tumour response.

- Pharmacokinetic analyses

All evaluable subjects will be included in the pharmacokinetic analysis. Subjects who are considered as not evaluable will be listed with their individual plasma concentrations and individual pharmacokinetic parameters, however, will not be included in descriptive statistics for plasma concentrations, pharmacokinetic parameters or other statistical assessment.

A subject is considered to be not evaluable if the subject has an important protocol violation relevant to the evaluation of pharmacokinetics or has insufficient data.

The following descriptive statistics will be calculated for analyte concentrations as well as for all pharmacokinetic parameters: N, arithmetic mean, standard deviation, minimum, median, maximum, arithmetic coefficient of variation, geometric mean, geometric coefficient of variation (refer also to 10.1).

Refer to Appendix 10.1 for details concerning handling and derivation of pharmacokinetic parameters.

If sufficient patients are entered into the study, covariates such as gender, age, and weight may be exploratively investigated for their potential influence on pharmacokinetic parameters. Exploratory analyses will compare the area under the plasma concentration-time profile and the maximum plasma concentration with considered relevant safety, efficacy, and pharmacodynamic endpoints.

- Efficacy analyses

Tumour response, objective response (CR, PR), and best overall response will be analysed descriptively according to the RECIST criteria (see section 5.1.2 and Appendix 10.4) at the end of every other treatment course.

For patients with no measurable lesion the overall response will be assessed as NEV (compare Table 10.4.4: 2). If data allow the assessment of the non-target lesion will be described in a explorative subgroup analysis.

The time to tumour progression will be defined as the time from first treatment administration to cancer progression or death due to the cancer under study.

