##### **3.3.1 Inclusion criteria**

- 1) Patients with confirmed diagnosis of advanced, non resectable and / or metastatic solid tumours, who have failed conventional treatment, or for whom no therapy of proven efficacy exists, or who are not amenable to established forms of treatment
- 2) Age 18 years or older
- 3) Written informed consent consistent with ICH-GCP and local legislation
- 4) Eastern Cooperative Oncology Group (ECOG, R01-0787) performance score  $\leq 2$
- 5) Recovery from CTCAE Grade 2 - 4 therapy-related toxicities from previous chemo-, hormone-, immuno-, or radiotherapies (except alopecia)

The 18 additional patients recruited at the MTD must also meet the following criterion:

- 6) Measurable tumour deposits (RECIST) by one or more techniques (CT, MRI)

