#### **10.4.3 Evaluation of non-target lesions**

Complete Response (CR): disappearance of all non-target lesions

Incomplete Response/ Stable Disease (SD): persistence of one or more non-target lesion(s)

Progressive Disease (PD): appearance of one or more new lesions and / or unequivocal progression of existing non-target lesions

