#### **10.4.4 Evaluation of best overall response**

The best overall response is the best response recorded from the start of the treatment until disease progression / recurrence (taking as reference for progressive disease the smallest measurements recorded since the treatment started). The patient's best response assignment will depend on the achievement of both measurement (overall response, Table 10.4.4: 1).

The overall responses for all combination of tumour response (target and non-target lesions) with and without appearance of new lesion is given in Table 10.4.4: 1

Table 10.4.4: 1 Overall responses for target and non-target lesions with and without appearance of new lesion

Target lesions	non-target lesions	new lesions	overall response
CR	CR	no	CR
CR	incomplete response / SD	no	PR
PR	non-PD	no	PR
SD	non-PD	no	SD
PD	any	yes or no	PD
any	PD	yes or no	PD
any	any	yes	PD

The examinations should be performed at screening and in line with RECIST after every second course of treatment if the patient qualifies for further courses. Tumour measurements at earlier time points after start of study treatment may be performed if clinically indicated as assessed by the investigator. Tumour measurements during the follow-up period after discontinuation of the study treatment are optional. Imaging results can be used at screening if they were done within the previous four weeks, i.e. no repeat investigation is requested for the purpose of the study.

To be assigned a status of CR, PR, or SD, changes in tumour measurements should be confirmed by repeat assessments that should be performed according to RECIST.

In the case that an assessment of the target and non-target lesion of a patient could not be made by the investigator the category "non-evaluable" (NEV) should be used. In case of absence of non-target lesion at baseline the category of NEV has to be used. The overall responses for all combination of tumour response (target and non-target lesions) with and without appearance of new lesion and non-evaluable lesion measurements is given in Table 10.4.4: 2

Table 10.4.4: 2 Overall responses for target and non-target lesions with and without appearance of new lesion and non-evaluable lesion measurements

Target lesions	non-target lesions	new lesions	overall response
NEV	Any, except of PD	no	NEV
NEV	PD	yes or no	PD
Any, except of PD	NEV	no	response criteria of target lesion
PD	NEV	yes or no	PD
any	any	yes	PD

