If the overall response is NEV the additional categories (NEVCNP and NEVCNP) will be used. Description see Table 10.4.4: 3. In the case that a tumour measurement was not performed please see handling of missing value (section 10.4.5).

Table 10.4.4: 3 Tumour response criteria in the case of no assessment of the tumour by the investigator

Label of tumour response	Shortcut	Tumour Response
Non-evaluuable, clinically not progressive	NEVCNP	No assessment of the tumour is possible, but the investigator rated the patient's disease status as clinically not progressive
Non-evaluuable, clinically progressive	NEVCP	No assessment of the tumour is possible, but the investigator rated the patient's disease status as clinically progressive

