5.2.2 Time-to-Event

Both, formal and informal summary analyses on time-to-event endpoints will be performed. That is to say, Kaplan-Meier analyses will be performed, and summary statistics will be calculated.

Progressive disease: Progressive disease (PD or NEVCPD) is level=5 as outlined in the endpoint 'Unconfirmed Overall Response' in [Section 5.2.1](#) above.

Date of progressive disease is the earliest of:

- 1) date of progression (progdt) recorded on course in e-CRF corresponding to first recurrence of progressive disease

- 2) date of progression recorded (progdt) on end of trial in e-CRF if first recurrence of progressive disease was at end of trial
- 3) date of progressive disease recorded on post-study follow-up of eCRF
- 4) death date (in the case of none of 1-3 being available)

Patients administered a new additional other anti-cancer therapy recorded in the e-CRF but not presenting with progressive disease before the start of this new anti-cancer therapy will be censored at the date of last radiological imaging before the new anti-cancer therapy has started.

Patients not administered another anti-cancer therapy and not presenting with progressive disease or death during the trial will be censored at the date of the last imaging during which the patient was evaluable and did not have the event. Alternatively, if there is an investigators assessment after this, then the date of the NEVCNPD will be used.

Progression-free survival (PFS) [in days] is therefore the time from first administration of trial medication to the earlier of progressive disease or death. (Date of PD as above – date of first administration of trial medication + 1).

Progression-free survival (PFS) censored [in days] is therefore the time from first administration of trial medication to the date of last imaging (or NEVCNPD as above). (Date of last imaging – date of first administration of trial medication + 1, or Date of NEVCNPD – date of first administration of trial medication + 1).

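### Protocol 7.3.2 scores the overall response of every patient without a measurable lesion as non-evaluable, which contradicts Table 10.4.4: 2, where non-target progression or a new lesion is PD

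*Protocol*

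**What the plan says.** Protocol 7.3.2 (efficacy analyses) says "For patients with no measurable lesion the overall response will be assessed as NEV", with a pointer to Table 10.4.4: 2, and leaves the non-target findings of these patients to an exploratory subgroup description if the data permit.

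The table it points to, in Protocol 10.4.4, is introduced as giving "The overall responses for all combination of tumour response (target and non-target lesions) with and without appearance of new lesion and non-evaluable lesion measurements". One row (target, non-target, new lesion, overall) reads "NEV PD yes or no PD". The last row makes any new lesion PD. Protocol 10.4.3 defines non-target PD as "appearance of one or more new lesions and / or unequivocal progression of existing non-target lesions".

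An overall NEV is then split into clinically progressive and clinically not progressive. The progressive category is defined as "No assessment of the tumour is possible, but the investigator rated the patient's disease status as clinically progressive"; the other has the same premise with the opposite rating.

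On who is affected, Protocol 3.3.1 says "The 18 additional patients recruited at the MTD must also meet the following criterion", namely measurable disease. No other patient has to meet it.

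SAP 5.2.1 analyses the overall-response answer on the eCRF together with clinical progression. It places NEVCNPD (non-evaluable, clinically not progressive) at level 4, and PD or NEVCPD (non-evaluable, clinically progressive) at level 5. Clinical Benefit is the absence of PD or NEVCPD during a course. In SAP 5.2.2, level 5 and death are events. A patient with neither, and with no other anti-cancer therapy, is censored at the last evaluable imaging: "Alternatively, if there is an investigators assessment after this, then the date of the NEVCNPD will be used".

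**The concern.** Two rules in one protocol give different answers for the same patient. Take someone with bone disease only, who feels well and whose scan after course 2 shows a new liver lesion. By 7.3.2 the overall response is NEV. By Table 10.4.4: 2 it is PD.

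The wording of 7.3.2 makes it hard to dismiss this as shorthand. It speaks of the overall response, not the target-lesion response, and it moves the non-target findings to an optional subgroup, which makes sense only if they do not determine the overall response.

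At stake are the PD counts by dose, Clinical Benefit, and the timing of PFS events, mainly in the escalation cohorts, where measurable disease is not an entry requirement.

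**Working it through.** No stated sample size, power or error rate bears on this point, so there is no plan figure to reproduce. The check is a classification exercise followed by a trace through the SAP.

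**1. Score every combination with target = NEV.**

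| Non-target | New lesion | Table 10.4.4: 2 | 7.3.2 read literally |
|---|---|---|---|
| CR | no | NEV | NEV |
| CR | yes | PD | NEV |
| Incomplete response/SD | no | NEV | NEV |
| Incomplete response/SD | yes | PD | NEV |
| PD | no | PD | NEV |
| PD | yes | PD | NEV |
| NEV | no | NEV | NEV |
| NEV | yes | PD | NEV |

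PD results: 5 of 8 under the table, 0 of 8 under the sentence. These are counts of combinations, not patient frequencies.

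**2. Follow the five discordant combinations into the SAP.** Suppose the eCRF entry is NEV.
- Rated clinically progressive: NEVCPD, level 5, still a PFS event.
- Rated clinically not progressive: NEVCNPD, level 4. This is not PD, it counts as Clinical Benefit for that course, and it is not a PFS event at that scan. A later recorded progression or death makes the event late. If neither occurs, the patient is censored.

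An effect on PFS therefore needs both an NEV entry despite radiological PD and a rating of clinically not progressive.

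**3. Exposure on the protocol's numbers.** Patients not required to have measurable disease: up to 80 − 18 = 62. Within the MTD group: 24 − 18 = 6.

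**4. Illustrative count; inputs assumed, not from the documents.** Events missed or delayed = 62 × f × q × c, where f is the share without a measurable lesion (10–30%), q the share of those with non-target or new-lesion PD (50–80%), and c the share of those coded NEV and rated clinically not progressive (0–100%).
- c = 0: 0 events.
- f = 0.1, q = 0.5, c = 1: 62 × 0.1 × 0.5 = 3.1.
- f = 0.3, q = 0.8, c = 1: 62 × 0.3 × 0.8 = 14.9.

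**5. Illustrative effect on PFS at day 84.** Assumed: exponential PFS with median 60 days, and half of the progressions in non-measurable patients seen only on imaging and coded NEVCNPD. Scans fall every 42 days (every other 21-day course). Let s be the non-measurable share of the analysed group.
- Progression probability per interval: 1 − 0.5^(42/60) = 0.384. True 84-day value: 0.616² = 0.379.
- Permanent censoring of image-only cases: (1 − 0.384 × (1 − 0.5s))². For s = 0.1, 0.2, 0.3 and 1 this gives 0.40, 0.43, 0.45 and 0.65.
- Image-only cases recorded one scan later: only those arising in the second interval are still counted as progression-free at day 84, so the value is 0.379 + s × 0.5 × 0.616 × 0.384 = 0.379 + 0.118s. For the same s: 0.39, 0.40, 0.41 and 0.50.
- All rated clinically progressive: no bias.

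**The case against.** The sentence in 7.3.2 cites Table 10.4.4: 2, and Protocol 5.1.2, which tells the investigator how to assess response, points to RECIST and Appendix 10.4. A reader who follows either reference reaches the PD rows. Reading NEV as the target-lesion entry reconciles the texts. Section 7.3.2 is analysis text, and nothing instructs an investigator to enter NEV when a new lesion is seen. The NEV sub-categories presuppose that the tumour could not be assessed, which does not describe a patient whose scan shows a new lesion. The readable SAP does not repeat the blanket rule, and part of its NEV algorithm is redacted.

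Most of this stands, and it limits the consequences. It does not remove the contradiction: the cross-reference does not say that the table prevails, and the literal sentence places patients in a category whose definition does not fit them.

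A reader might go further and infer that real progressions are lost from the PD counts and from PFS. The documents do not support that. The protocol's own endpoint is time to progression, defined by cancer progression or cancer death and not by a response code. PFS appears only in the SAP, where NEVCPD, recorded progression dates and deaths are all events. Nor is 62 of 80 an estimate of patients affected; it is a ceiling on those not required to have measurable disease. SAP 7.5 plans Kaplan-Meier analyses, if applicable, for the MTD group and other cohorts of interest, and at the MTD at most 6 of 24 are exempt from the criterion.

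**Conclusion.** The contradiction is real: 5 of 8 target-NEV combinations are PD under Table 10.4.4: 2 and none under the literal sentence in 7.3.2. Followed literally, and only when the patient is also rated clinically not progressive, it can lower the descriptive PD count, add to Clinical Benefit, and delay or censor a PFS event.

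The number of patients cannot be determined. The documents give neither the rate of non-measurable disease nor the share of progressions seen only on imaging, and the redacted SAP algorithm may already deal with these cases. The illustrations show only a possible range: 0 to about 15 events, and an 84-day value within non-measurable patients between the true 0.38 and a worst case of 0.65, or about 0.50 if events are merely one scan late. They rest wholly on the assumed inputs. The endpoints are secondary and descriptive, with no formal inference planned, and the MTD does not depend on them.

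**What to change.** Replace the sentence in Protocol 7.3.2 with wording such as: *Where a patient has no measurable lesion, the target-lesion response is NEV and the overall response follows Table 10.4.4: 2 (PD if non-target lesions progress or a new lesion appears, otherwise NEV).*

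In the same edit, reconcile Protocol 5.1, which describes efficacy in patients with measurable disease, with Protocol 7.3, which uses the treated set, so that it is clear whether these patients enter the efficacy tables.

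In the SAP, it is enough to confirm that the NEV algorithm in 5.2.1 puts non-target PD or a new lesion at level 5 for these patients. Add text only if it does not.

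The cost is small: one protocol sentence, one reconciliation and one check. Non-target and new-lesion status are already part of the tumour assessment, so no new data are needed. The downside is that PD counts and PFS may look slightly less favourable.

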## CLINICAL TRIAL PROTOCOL SYNOPSIS

Name of company: [REDACTED]		Tabulated Trial Protocol			
Name of finished product: NA					
Name of active ingredient: BI 6727					
Protocol date 03 October 2005	Trial number 1230.1	Planned study period 10/2005 – 02/2007			
Title of study: An open phase I single dose escalation study of BI 6727 administered intravenously in patients with advanced solid tumours with repeated administration in patients with clinical benefit					
Investigator : [REDACTED]					
Study centre : [REDACTED]					
Clinical phase: I					
Objectives: Safety, maximum tolerated dose (MTD), pharmacokinetics, efficacy					
Methodology: Uncontrolled, open label, dose escalation					
No. of subjects entered:					
total:	Up to 80				
each treatment:	3 to 6 per level, 24 at MTD				
Diagnosis and main criteria for inclusion Patients with a confirmed diagnosis of an advanced and/or metastatic solid tumour refractory to standard therapy or not amenable to standard therapies					
Test product(s) : BI 6727					
dose:	Start dose of 12 mg				
mode of admin. :	Intravenous, once every 21 days				
Reference therapy: n.a.					
dose:					
mode of admin. :					
Duration of treatment: Single dose, repeated treatment courses in patients with clinical benefit					
Criteria for efficacy: Tumour response, time to progression, pharmacokinetic profile of BI 6727					
Criteria for safety: Adverse events according to common terminology criteria for adverse events (CTCAE) v.3.0, laboratory evaluations, patient performance, vital signs					
Statistical methods: descriptive statistics					
Kaplan Meier method for time to progression analysis					

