### 2.3 SECONDARY ENDPOINT(S)

- 1) Incidence and intensity of drug-related adverse events according to common terminology criteria for adverse events (CTCAE) v.3.0, laboratory evaluations, patient performance and vital signs
- 2) Tumour responses and time to progression after BI 6727 treatment
- 3) Pharmacokinetic parameters of BI 6727 (for parameters cf. section 7.1.2.).

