#### 7.4 HANDLING OF MISSING DATA

Every effort will be made to obtain complete information on all adverse events, with particular emphasis on potential dose limiting toxicities.

If not stated otherwise, missing data will not be imputed and remain missing. Potential outliers will be reported and analysed as observed.

Tumour evaluation : see RECIST criteria (see ISF, R01-0754) and Appendix 10.4.5 "Handling of missing tumour lesion measurement".

Time to progression:

Patients for whom no tumour assessments are available within the six weeks prior to discontinuation from treatment will be examined on a case by case basis. In case of early stop not related to the disease, patients will be censored at time of EOT.

Pharmacokinetic evaluation: For details refer to Appendix 10.1.

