4. CHANGES IN THE PLANNED ANALYSIS OF THE STUDY

Some newly created endpoints regarding tumour response are created and explained within the TSAP.

Following Amendment 3, a more extensive analysis of electrocardiograms (ECG) is planned on the additional cohort of 14 patients. The main aim of this cohort was to investigate QTc changes in parallel with PK sampling during and after intravenous infusion of BI 6727 300 mg dose over 1 hour and over 2 hours. For this set of 12 patients a different analysis of ECG data is planned (see [Section 7.7.4.1](#)).

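### The SAP analyses progression-free survival where the protocol names time to progression, censors some early stops differently, and does not name either change in its Section 4

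*Protocol*

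**What the plan says.** **Protocol.** Section 2.3 lists "Tumour responses and time to progression after BI 6727 treatment" among the secondary endpoints, and the synopsis plans the "Kaplan Meier method for time to progression analysis". Section 7.3.2 defines the quantity as "time from first treatment administration to cancer progression or death due to the cancer under study". Section 7.4 adds: "In case of early stop not related to the disease, patients will be censored at time of EOT". It sends patients with no tumour assessment in the six weeks before discontinuation to case-by-case review, and states no general censoring rule for anyone else.

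**SAP.** Section 5.2.2 defines one time-to-event endpoint, PFS, as the "time from first administration of trial medication to the earlier of progressive disease or death". Cause of death is not restricted, and a death date serves as the progression date when no progression date exists. A patient with no event and no new anti-cancer therapy "will be censored at the date of the last imaging during which the patient was evaluable and did not have the event", or at the date of a later investigator assessment of non-evaluable but clinically non-progressive disease (NEVCNPD). A patient who starts new therapy without progression is censored at the last imaging before it. Section 7.5 plans Kaplan-Meier for PFS alone, if applicable, in the MTD group and other cohorts of interest.

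**List of changes.** SAP Section 4 says "Some newly created endpoints regarding tumour response are created and explained within the TSAP" and then describes the added ECG analysis. It does not mention TTP, PFS or censoring.

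**The concern.** A reader who follows the protocol expects TTP. A reader who follows the SAP gets PFS. In a first-in-human trial that escalates until toxicity appears, a death from toxicity or intercurrent illness is possible. Such a death is an event in the SAP's endpoint and not in the protocol's. If one occurs, the PFS curve partly measures tolerability, and nothing in the report would answer the protocol's question about the tumour.

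The censoring difference compounds this, because the same early-stopping patient can have a different follow-up time under each document. SAP Section 4 is where a reader would look for such changes, and it names neither.

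**Working it through.** The plan states no figure for this endpoint, so the check is mainly a comparison of text.

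**1. Events** (Protocol 7.3.2 against SAP 5.2.2)

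| First occurrence | Protocol TTP | SAP PFS |
|---|---|---|
| Progression | event | event |
| Death from the cancer under study, no progression recorded | event | event |
| Death from another cause, no progression recorded | not an event | event |

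Only the third row separates the two definitions.

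**2. How much the third row could matter.** The documents give no number of such deaths, so this is an illustration under assumptions that are not in them. Take constant hazards: λ for progression or cancer death, and μ for other deaths. Let f = μ/(λ + μ) be the share of first events that are other deaths. Then λ + μ = λ/(1 − f), and

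median PFS = ln 2/(λ + μ) = (1 − f) × ln 2/λ = (1 − f) × median TTP.

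| Assumed median TTP | f = 0 | f = 0.05 | f = 0.10 | f = 0.20 |
|---|---|---|---|---|
| 60 days | 60 | 57.0 | 54.0 | 48.0 |
| 90 days | 90 | 85.5 | 81.0 | 72.0 |

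With no such deaths the event definitions give the same result. At f = 0.20 the median falls by a fifth.

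**3. Censoring**

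| Patient without an event | Protocol 7.4 | SAP 5.2.2 |
|---|---|---|
| Early stop not related to the disease | EOT | last evaluable imaging, or later NEVCNPD date |
| New anti-cancer therapy before progression | no specific rule | last imaging before the therapy |
| Others | no general rule | last evaluable imaging, or later NEVCNPD date |

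The direct conflict is in the first row. Where the protocol has no rule, the SAP fills a gap.

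The size of the date shift is not fixed:
- Routine imaging follows every second 21-day course, so scans are about 2 × 21 = 42 days apart on treatment.
- Protocol 6.2.3 asks for imaging at end of trial unless it was done within the past three weeks, which would shorten the gap to EOT to about 21 days. The flow charts mark no imaging at EOT.
- Follow-up imaging can come after EOT, although Appendix 10.4.4 calls it optional. The SAP date could then be later than the protocol date.

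**4. The SAP formula.** Censored time = date of last imaging − date of first dose + 1. Protocol 6.2.1 accepts screening scans up to four weeks old, and SAP Table 6.2: 1 counts four weeks back from treatment. If such a scan is the only evaluable one:

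- scan 1 day before first dose: −1 + 1 = 0 days
- scan 28 days before first dose: −28 + 1 = −27 days

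This needs a patient with no later evaluable scan, no NEVCNPD date, no progression and no death. A censored time at or before zero does not move the Kaplan-Meier curve. SAP 5.2.2 also plans summary statistics, and the value could enter those.

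**The case against.** The strongest objection concerns what is not in the file. The SAP implements the 2005 protocol and three amendments up to June 2008. It already describes features absent from the supplied protocol, such as the 300 mg QTc cohort, the 2-hour infusion and a second centre. An amendment may have replaced TTP or revised the censoring, and Section 4 would then have had nothing of its own to declare. Parts of the SAP are also redacted, including text next to the rule for missing progression dates. This stands, and it limits confidence. It does not remove the mismatch between the two documents as supplied.

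It can also be said that the sentence in Section 4 on new response endpoints covers PFS, because progression is defined from one of those endpoints. That is a generous reading. PFS sits under its own time-to-event heading, and the sentence names neither an endpoint replaced nor a censoring rule.

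Three stronger readings are tempting, and the documents do not support them:
- **That censoring dates move back by up to six weeks.** The end-of-trial imaging instruction and possible follow-up scans leave both size and direction open.
- **That the effect can be put at, say, two deaths among the 24 MTD patients.** No document gives such a count, and 2/24 = 8.3% would be a share of patients, not of events.
- **That the endpoint was switched after results were seen.** The trial is open label and the SAP uses the past tense, but nothing dates or explains the change.

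Finally, the endpoint is secondary, and both documents call all analyses descriptive. That stands and lowers the priority.

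**Conclusion.** The point holds as a mismatch in endpoint and documentation. As supplied, the protocol promises TTP with cancer deaths only, the visible SAP delivers only PFS with all deaths, and Section 4 does not name the change. The effect is nil if no patient dies of another cause before progression. Otherwise its size is unknown; the medians above rest on constant hazards and an assumed share of 5% to 20%.

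The censoring rules conflict for early stops not related to the disease and, on this text, for no one else. The zero or negative time is a corner case, but it follows directly from the formula and no visible rule prevents it.

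A reader might conclude that TTP is never analysed anywhere. The documents support less: no TTP analysis appears in the readable SAP. Importance is modest and confidence moderate.

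**What to change.** - **SAP 5.2.2 and 7.5:** add TTP with the protocol's event definition beside PFS, with deaths not due to the cancer under study censored.
- **Censoring:** use one rule for both endpoints. If it is the imaging-based rule, say that it replaces Protocol 7.4 for early stops not related to the disease, and do not present it as the protocol's own definition.
- **Floor:** set the censoring time to day 1 for event-free patients with no post-baseline assessment.
- **SAP Section 4:** list the added PFS endpoint and the censoring change with reasons, or cite the amendment that made them.

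The cost is SAP wording and one extra derived variable. Deaths must also be classified by cause. The documents list no dedicated cause-of-death field, so this would draw on the adverse event outcomes and drug-relationship assessments (Protocol 8.4.1) and on the progression records kept in the eCRF (Protocol 5.2.2). Trial conduct does not change.
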